In those with posttraumatic stress disorder (PTSD), trauma-related nightmares are a hallmark re-experiencing symptom and a common and severe source of distress often resulting in re-traumatization due to the lack of insight afforded by wakefulness. Proposed research will examine whether such nightmares might serve as targets for imaginal exposure during prolonged exposure therapy (PE), a first line treatment for PTSD. PE produces significant PTSD symptom reduction. However, approximately 30% of patients prematurely drop out from PE treatment and most still meet diagnostic criteria for PTSD at end of treatment. Thus, means for increasing the efficacy of PE are important areas of investigation. Fear extinction learning and memory are the neurocognitive underpinnings of PE. Because increased physiological arousal during PE can aid in extinction learning, recall of trauma-related nightmares might serve as an effective target for PE because of their greater immediacy and salience relative to the more temporally distant traumatic event. Our research group has developed standardized script-driven imagery (SDI) procedures whereby the degree of psychophysiological arousal induced by recollection of the traumatic event that precipitated posttraumatic symptoms (index trauma) can be assessed in those with PTSD. A canonical variable for physiological reactivity to SDI (SDI-PR) is derived from skin conductance (SC), facial electromyography (EMG) and electrocardiography (ECG) and has served as a unitary, objective measure capable of distinguishing those with versus without clinician-diagnosed PTSD. Members of our team have also developed a novel ambulatory device, the NINscan, that can record SC, EMG and ECG along with simultaneous functional near-infrared spectroscopic (fNIRS) imaging of the lateral prefrontal cortex (LPFC). fNIRS yields concentrations of oxygenated ( $O_2Hb$ ) and deoxygenated (HHb) hemoglobin that can be used to assess cortical activation. Specific areas of the LPFC have been shown to activate and/or deactivate during SDI of an index trauma in persons with PTSD. Notably, the LPFC includes the right inferior frontal gyrus (rIFG), a region shown to play a prominent role in inhibiting unwanted behavior and cognition, in which reduced activation accompanies reduced inhibitory performance in persons with PTSD, compared to controls. In participants with PTSD and trauma-related nightmares, proposed research will compare psychophysiological responses and LPFC activation between SDI of a recent trauma-related nightmare versus SDI of the index trauma. During nights over a 2-week period, participants will audio-record timestamped nightmare reports following all nightmare-induced awakenings. During two to four such nights, ambulatory polysomnography (PSG) will allow analysis of sleep physiology immediately preceding nightmare awakenings. A trauma-related nightmare report having sufficient length, clarity and resemblance to the index trauma will be selected and recorded as a script for SDI. The overarching goal of the proposed research will be to compare within-subject similarities and differences in brain and autonomic activation between imaginal replay of a trauma-related nightmare versus imaginal replay of the index trauma to determine the relative degree to which each evokes autonomic and frontocortical activations.

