## STUDY PROCEDURES

**Overview of protocol:** The protocol consists of screenings followed by 3 experimental Phases. Individuals diagnosed with PTSD who report frequent TRNs will be recruited from the MGH-Red Sox Foundation's Home Base program, the Boston VA Medical Center, local hospital trauma clinics, and from the community. Interested individuals will first complete a telephone screening followed by a series of structured clinical interviews using a Zoom Healthcare Secure Room to diagnose PTSD and comorbid psychiatric disorders, confirm initial inclusion criteria, rule out exclusion criteria and create an audio-recorded account of their index trauma. Participants passing screenings will then proceed to Phase 1 and complete 2 weeks of at-home sleep and nightmare diaries and time-stamped audio-recorded reports of dream content upon awakening from any nightmare. They will also wear a wrist actigraph throughout this period, complete two to four nights of ambulatory PSG, and complete on-line guestionnaires. Nightmare data will be examined for frequency and thematic similarity of nightmares to a participant's reported index trauma. Those reporting at least 4 such nightmares with at least one that is clearly related to the index trauma and sufficiently detailed for script creation will be invited to participate in Phase 2. Phase 2 participants will undergo a structural MRI scan and will then be scheduled to undergo MRI-guided positioning of fNIRS sources and optodes using the BrainSight2 System. Phase 3. Participants' nightmare and index trauma reports will be audio-recorded for use as scripts during SDI. The participant will then undergo two SDI sessions on a single day, one with a nightmare script and one with an index-trauma script, during which they will wear the NINscan. Sessions will be separated by 1 hour and counterbalanced across participants for script order.

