**Phase 2:** Participants will undergo a structural T1 MPRAGE MRI scan. This will be used along with the BrainSight Frameless Stereotactic System (Rogue Research, Inc., Montreal, CN) to localize fNIRS optodes at 8 bilateral regions of interest (ROIs) (4 per hemisphere) including the frontopolar cortex (BA 10), as well as superior (BA 9), middle (BA 46) and inferior (BA 47) frontal gyri.

**Phase 3:** When we capture a suitable nightmare from a participant, the recorded nightmare report will be transcribed and audio-recorded by an investigator as a TRN script following our standard procedures. Participants will then come to the laboratory and complete 2 SDI sessions with NINscan monitoring, one of which will use the script derived from the TRN and the other the script derived from the index trauma. Presentation order of the scripts derived from the TRN and from the index trauma will be counterbalanced across participants. Because PTSD symptomatology and extinction memory may vary with the menstrual cycle, female participants not on oral contraceptives will undergo SDI during the early follicular phase of their cycle.

**Script Driven Imagery**: Adapting standardized SDI protocols, scripts will be created from audio-recorded accounts of the index trauma about which a participant's TRNs represent a re-experiencing. The audio-recorded report and list of bodily sensations experienced from an awakening during Phase 1 will provide material for the nightmare script. Account of a second personalized stressful event unrelated to the index traumatic event will be similarly recorded as well as one recording each of a recalled positive and emotionally neutral experience. These accounts will be transcribed and the subject will clarify and expand on details as necessary. Scripts approximately 30 sec in duration will then be composed and recorded by experienced staff, portraying each experience in the second person, present tense. Six 30-sec standard generic scripts of both neutral and emotional situations (2 each of neutral, fearful and positive

experiences) will also be recorded. Script recordings will be played to participants through headphones as they vividly imagine each event and physiological data are continuously sampled.

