**Actigraphy and sleep diary:** The waterproof Actiwatch 2 (Philips Respironics, Bend, OR) is worn on the non-dominant wrist 24h/day and counts arm movements in 1-min epochs. Participants press an event marker when beginning to attempt sleep and when waking for the day. Epochs are scored as sleep or wake using a standardized algorithm. The EMSQ queries daytime activities and the time one begins attempting sleep (evening), and wake time, subjective sleep latency, total sleep time, and number of awakenings (morning).

**Self-report assessments:** A secure online MGH system will obtain the: 1.) Pittsburgh Sleep Quality Index  with PTSD addendum; 2.) Insomnia Severity Index; 3.) Morningness-Eveningness questionnaire; 4.) Spielberger State-Trait Anxiety Inventory; and 5.) Inventory of Depressive Symptomatology.

**Outcome and predictor variables:** For Hypothesis 2, outcomes will be "difference scores" between biosignals from the 30-s trauma-related epoch of the nightmare and index-trauma SDI and their baseline epochs (30 s of silence preceding the respective script). For fNIRS, the quantities used to compute difference scores will be  $O_2$ Hb minus HHb concentrations (HbD)

at each ROI. Peripheral outcome will be SDI-PR computed from HR, SC and EMG responses to the index trauma and nightmare scripts. Primary outcome of Exploratory Hypotheses 1A and 1B will be whether or not SDI-PR and HbD are larger in response to trauma-nightmare SDI than to index trauma SDI. Predictor variables for Exploratory Hypothesis 1A will be sleep stage prior to awakening from trauma nightmare. Predictor variables for Exploratory Hypothesis 1B will be ratings by 3 judges, blind to all other participant data, on two 7-point Likert-type scales of 1) the degree of similarity between each individual's index-trauma and trauma-nightmare scripts, and 2) the emotional severity of the recorded trauma-nightmare experience.

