Statistical analyses: As feasibility assessments of NINscan methodology, Hypothesis 1 The gualitative optimization of NINscan's biosensor configuration, biosignal acquisition, event marking, and interface with software delivering SDI stimuli, rather than quantitative hypothesis testing, is the focus of Aim 1. To test Hypothesis 2, the two primary outcome variables (rIFG fNIRS HbD and SDI-PR) will be compared between trauma-nightmare and index-trauma SDI using multiple regression adjusting for age, sex and duration since trauma. Secondary outcome variables (HbD from the 7 remaining fNIRS ROIs) will be compared between groups using the same regression model as for the primary fNIRS outcomes adjusting for multiple comparisons using the false discovery rate. Analysis of Exploratory Hypothesis 1A: We will investigate whether a stronger response to the trauma-nightmare as compared to the indextrauma script is associated with REM sleep using logistic regression, with REM sleep (0/1), sex (M/F) and duration since trauma as predictors. Analysis of Exploratory Hypothesis 1B: The similarity between the trauma-nightmare and index-trauma scripts and the severity of the trauma-nightmare script will be evaluated for each subject by 3 judges using 7-point Likert scales. The relationship between these evaluations and a greater SDI-PR or rIFG HbD response to trauma-nightmare than index-trauma SDI will be assessed using ordinal regression, with sex, judge ID, and duration since trauma as additional covariates.

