**Power analysis:** For the primary outcome in Aim 2, we will compare physiological response and fNIRS in the rLIFC between scripts for the index trauma and the associated nightmare in each of 40 subjects completing the study (i.e., dropouts will be replaced). Based on a paired t-test at the 0.05/2 two-tailed significance level (adjusting for the two outcome measures), we will have 80% power to detect an effect size of d=0.50. In order to power the hypothesis in Exploratory Aim 1, we first assume that each of 50 subjects have one nightmare and that 60% of these nightmares will occur during REM sleep. For this situation, we will have 80% power to detect whether the probability of having greater SDI-PR or rIFG HbD response to the traumanightmare, compared to the index-trauma script is 0.70 or greater for patients who had nightmares during REM sleep, and 0.30 or less for those whose nightmares were not during REM sleep, based on Fisher's exact test, at the 0.05 two-tailed significance level.

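### The Hypothesis 2 regression does not say how a participant's two responses are paired and omits script order, although the design is within-person and counterbalanced and the 80% power rests on a paired t-test.

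*Combined protocol and SAP*

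**What the plan says.** - **Primary analysis** (Statistical analyses, Hypothesis 2): the two primary outcomes "will be compared between trauma-nightmare and index-trauma SDI using multiple regression adjusting for age, sex and duration since trauma". No other term is named.
- **Secondary analysis** (same section): HbD at the seven other regions "will be compared between groups using the same regression model as for the primary fNIRS outcomes", with false discovery rate control.
- **Outcomes** (Outcome and predictor variables): the difference scores are taken "between biosignals from the 30-s trauma-related epoch of the nightmare and index-trauma SDI and their baseline epochs". Each script has its own baseline, so a participant contributes two scores per outcome.
- **Design**: the stated goal in the opening overview is to "compare within-subject similarities and differences in brain and autonomic activation". The Overview of protocol adds: "Sessions will be separated by 1 hour and counterbalanced across participants for script order". Phase 3 repeats that script order is counterbalanced.
- **Power** (Power analysis): 80% power for d=0.50 in 40 completers. "Based on a paired t-test at the 0.05/2 two-tailed significance level (adjusting for the two outcome measures"). The Recruitment and Retention sections set the completer target at 50.

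**The concern.** The design and the power calculation are paired, but the analysis text gives no way for the pairing to enter the model. Age, sex and duration since trauma do not vary within a person, so adjusting for them cannot stand in for a participant term. The baseline-corrected scores do not supply the link either, because each is a script epoch minus its own silence, not nightmare minus index. The phrase about comparing groups in the secondary analysis points, if anything, towards an unpaired model, although the study has no groups.

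Aim 1 is qualitative, so this is the trial's main quantitative test. One analyst could regress the within-person difference and another could stack two rows per person. Both would be following the text, and they would report different p-values from the same data. Script order is controlled by design and then appears in no model, so any shift between the first and second session is left in the error term.

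**Working it through.** **Inputs from the documents.** n=40 (Power analysis) and n=50 (Recruitment, Retention); d=0.50, read as the mean paired difference over the SD of the paired differences; alpha 0.05/2 = 0.025, two-sided. The within-person correlation ρ between a participant's two responses is not given, so a range from 0 to 0.7 is assumed.

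**1. The stated power.** For a paired t-test the noncentrality is d√n, with n−1 degrees of freedom.
- n=40: 0.50 × √40 = 3.162; critical value 2.331 (39 df); exact power 79.3%.
- n=50: 0.50 × √50 = 3.536; critical value 2.312 (49 df); exact power 88.5%.

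The stated 80% is therefore reproduced for a paired test.

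**2. The regression run literally.** Take two rows per person; script, age, sex and duration as predictors; no participant term. Set the outcome variance to 1. A paired d of 0.50 then corresponds to a script effect of 0.50 × √(2(1−ρ)). The true standard error of the script contrast is √(2(1−ρ)/n), but the model uses about √(2/n), which is too large by a factor 1/√(1−ρ). With t* the critical value on 2n−5 df, approximately:

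power ≈ Φ(0.50√n − t*/√(1−ρ))

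At n=40, t* = 2.287 (75 df):
- ρ=0.3: 3.162 − 2.287/√0.7 = 3.162 − 2.734 = 0.428, giving 67%.
- ρ=0.5: 3.162 − 2.287/√0.5 = 3.162 − 3.235 = −0.073, giving 47%.

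Simulation (20,000 runs for power, 60,000 for type I error), which also allows for estimating the residual variance, gives:

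| ρ (assumed) | 0 | 0.1 | 0.2 | 0.3 | 0.5 | 0.7 |
|---|---|---|---|---|---|---|
| Power, n=40 | 81.3% | 77.2% | 72.5% | 66.7% | 49.4% | 19.2% |
| Type I error, n=40 | 2.45% | 1.84% | 1.23% | 0.87% | 0.22% | 0.02% |
| Power, n=50 | 89.8% | 86.9% | 84.0% | 79.1% | 64.0% | 29.3% |
| Power, n=40, covariates explain 30% of between-person variance (assumed) | 80.9% | 78.9% | 75.5% | 71.4% | 58.6% | 32.0% |
| Power, n=50, same assumption | 89.4% | 87.5% | 85.6% | 82.1% | 71.4% | 46.4% |

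**3. Script order.** Suppose the second session differs from the first by s, in units of the SD of the paired difference. With balanced orders this moves half the differences up by s and half down. Their mean is unchanged, but their SD is inflated by √(1+s²). For a paired t-test without an order term, approximately:

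power ≈ Φ(0.50√n − t*√(1+s²)), with t* now on n−1 df

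At n=40:
- s=0.5: 3.162 − 2.331 × 1.118 = 0.556, giving 71%.
- s=1.0: 3.162 − 2.331 × 1.414 = −0.135, giving 45%.

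Simulation (20,000 runs):

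| Session shift s (assumed) | 0 | 0.25 | 0.5 | 1.0 |
|---|---|---|---|---|
| No order term, n=40 | 79.7% | 77.1% | 70.5% | 44.5% |
| No order term, n=50 | 88.4% | 87.4% | 82.2% | 58.8% |
| Difference model with order and centred covariates, n=40 | 79.3% | 78.8% | 79.2% | 79.1% |

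At n=50 the model with order stays at 87.8% to 88.6%. Testing script type with a session term within persons (n−2 df) gives 78.8% to 79.6% at n=40 and 88.5% to 88.8% at n=50. With no session shift, the order term has no measurable cost.

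**The case against.** The strongest reply is that the plan, read as a whole, is paired. The overview sets a within-person goal, the Power analysis uses a paired t-test for the same outcomes, and a regression of the nightmare-minus-index difference also fits the words used. On that view the power losses in the first table arise only if an analyst ignores the rest of the document. The reference to groups can only mean script conditions, and it appears only for the secondary regions. This largely stands: pairing is unstated rather than rejected, and the losses are conditional on the literal reading. It does not remove the gap. Even the difference model is unspecified as written: its intercept is the mean script effect only if the covariates are centred, and the text does not say which coefficient is tested.

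Other points also stand:
- A paired t-test has no order term, so the order omission is a mismatch with the counterbalanced design and not with the power calculation.
- Counterbalancing already protects the mean contrast from a simple session shift. The shifts are assumed, and at 0.25 SD the cost is about 2 points.
- Baseline subtraction removes stable additive differences between people, so a high within-person correlation cannot be presumed.
- At n=50 the 80% is roughly met up to a correlation of 0.3.
- With positive correlation the literal model is conservative, so no false-positive claim is at risk.

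**Conclusion.** The concern holds and should be fixed. The only analysis text for Hypothesis 2 gives neither a pairing structure nor an order term, while the design is within-person and counterbalanced and the power claim is paired. Under the literal two-row reading, the stated 80% at n=40 is kept only when the within-person correlation is close to zero, and power falls to about half at a correlation of 0.5. At 50 completers it holds to about 0.3. The harm is a missed effect. These sizes rest on the assumed correlations and on a paired d of 0.50, and they shrink if the covariates explain between-person variance. The order effect is a matter of precision, and its size depends on an assumed session shift. What does not depend on any assumption is that the text permits analyses giving different p-values from the same data.

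**What to change.** Name one model in advance for Hypothesis 2:

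- **Either** a linear mixed model with a random participant intercept and fixed effects for script type, session (first or second), age, sex and duration since trauma, testing script type at 0.025 for each primary outcome;
- **or** a regression of the nightmare-minus-index difference on sequence (coded ±0.5) and mean-centred age, sex and duration, testing the intercept at 0.025.

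The two are not identical, because in the difference model the covariate coefficients are script-by-covariate interactions. Either is acceptable, but only one should be named. Apply the same model to the seven secondary regions with the planned false discovery rate control, and reword that comparison as being between scripts within participants.

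The cost is one or two sentences and one degree of freedom for order. No new data are needed, and power at n=40 stays at about 79% with either model.

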Increased physiological arousal during prolonged exposure therapy (PE) can facilitate extinction learning. Hence recall of TRNs might serve as an effective target for PE because of their greater immediacy and salience relative to the more temporally distant traumatic event. Enhancement of extinction learning by increased arousal is a documented phenomenon in experimental and clinical paradigms. For example, sustained self-reported arousal during exposure therapy for Social Anxiety Disorder (SAD) predicted superior treatment outcome. Similarly, enhanced exposure treatment for SAD has been reported with administration of Yohimbine, an alpha-2 agonist that increases noradrenergic neurotransmission and arousal. In PE, the focus on "hot spots" is a naturalistic example of increasing arousal during exposure. Therapists typically direct patients to focus on "hot spots" after the initial recounting of the trauma from start to finish. Hence, we hypothesize that if trauma-nightmare SDI elevates responding above that produced by the index-trauma SDI, imaginal trauma-nightmare exposure could improve PE treatment outcome.

TRNs rarely occur in the sleep laboratory. Consequently, information on their physiological associates during sleep is limited and knowledge of their brain substrates is entirely lacking. Although there have been laboratory and ambulatory studies in which TRNs were recorded using standard polysomnography (PSG), none have achieved a large sample or imaged brain activity. This motivates our proposed exploratory use of simultaneous PSG and functional near-infrared spectroscopic (fNIRS) imaging techniques. Although REM may be more conducive to the occurrence of TRNs, a significant percentage can arise from NREM, especially N2. The two most successful attempts to record the physiology of TRNs used ambulatory PSG, one of which reported 57% of nightmares from REM and 37% from NREM sleep. Arousals resulting in nightmare reports are often accompanied by sleep-disruptive events such as apneas, leg movements, startle-like arousals, excessive body movements and phasic sympathetic activation.

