#### Importance of the knowledge to be gained:

During PE for PTSD, trauma-related nightmares might offer targets for exposure treatments that are of greater immediacy and salience than the more temporally distant index trauma that originally precipitated an individual's PTSD. As such, use of trauma-related nightmares might strengthen arousal during PE and thereby enhance therapeutic extinction leading to greater reductions in PTSD symptoms. The proposed research will provide preliminary evidence as to whether or not this is the case by comparing both autonomic and brain responses to script-driven imagery of the original traumatic experience to script-driven imagery of a recent trauma-related nightmare. Additionally, the ability to assess activity in the LPFC during SDI might provide crucial information relating to individual differences in treatment response. For example, greater engagement of the LPFC following transcranial magnetic stimulation has been shown to predict treatment outcome from PE in PTSD. Moreover, the Phase-4 participants will provide the first glimpse into LPFC activity during nightmares, and could generate hypotheses on potential methods to assess treatments of nightmares (pharmacological or behavioral) in naturalistic settings.

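### The Hypothesis 2 regression names no pairing term, and its covariates, constant within each participant, cannot change the nightmare-versus-index contrast as main effects

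*Combined protocol and SAP*

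**What the plan says.** The design is within-subject. The overview under Study Procedures states: "The participant will then undergo two SDI sessions on a single day", one per script, with order counterbalanced.

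Under Statistical analyses, the two primary outcomes (rIFG HbD and SDI-PR) are compared between scripts "using multiple regression adjusting for age, sex and duration since trauma". The seven remaining fNIRS regions "will be compared between groups using the same regression model as for the primary fNIRS outcomes", with false discovery rate control. No pairing term, random intercept or script-by-covariate interaction is named.

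Under Outcome and predictor variables, the Hypothesis 2 difference scores are taken between the script epochs "and their baseline epochs (30 s of silence preceding the respective script". They are therefore script minus baseline, not nightmare minus index, and each participant contributes two of them per outcome.

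The Power analysis uses a different method: "Based on a paired t-test at the 0.05/2 two-tailed significance level (adjusting for the two outcome measures"), for which "we will have 80% power to detect an effect size of d=0.50" with 40 completers. The Recruitment section sets the target at 50 completers.

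The Significance section motivates the nightmare script by its "greater immediacy and salience relative to the more temporally distant traumatic event", and the section on the importance of the knowledge repeats the argument. Duration since trauma also appears as a predictor in the Exploratory 1A logistic model and as a covariate in the 1B ordinal model.

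**The concern.** Age, sex and time since trauma describe the participant, not the script. A participant's two responses share them, so they cannot confound a comparison made within that participant, and entering them as main effects cannot adjust it.

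The larger issue is what kind of regression is meant. Two baseline-corrected scores per person, a comparison described as being between groups, and no pairing term together allow an ordinary regression on stacked script-level rows. That model leaves the variation between participants in the error term. Its error bars would then not match the paired test on which the trial was sized. The same model is reused for all seven secondary regions, so any loss carries through.

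**Working it through.** **Inputs.** From the Power analysis: n=40, d=0.50, two-sided alpha 0.025 per outcome. From Recruitment: n=50. The documents give no within-person correlation, so 0.3, 0.5 and 0.7 are assumed. The simulations also assume age uniform over the eligible 18-60 years, half the sample female, and a skewed duration since trauma averaging about 10 years.

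**1. The plan's own figure.** For a paired t-test with n=40, the noncentrality is 0.50 × √40 = 3.162 on 39 degrees of freedom. Exact power is 79.3% (normal approximation 82.1%), so the stated 80% reproduces. With n=50, exact power is 88.5%.

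**2. Main-effect covariates.** Code script s as 0 or 1 and let z be any participant-level covariate. The cross-product of centred script with z, summed over a participant's two rows, is z × (−½) + z × (+½) = 0. Script is therefore orthogonal to every such covariate, and the script coefficient is the raw mean paired difference. In one simulated set of 50 complete pairs:

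| Model | Script coefficient | SE |
|---|---|---|
| Stacked OLS, no covariates | 0.233653 | 0.235 |
| Stacked OLS, three covariates | 0.233653 | 0.212 |
| Random intercept, with or without covariates | 0.233653 | 0.15484 |
| Paired t-test | 0.233653 | 0.15484 |

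The covariates move only the SE of the unpaired model, which stays above the paired SE.

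**3. Cost of ignoring pairing.** With residual variance σ² and within-person correlation ρ, the true variance of the contrast is 2σ²(1−ρ)/n, but stacked OLS estimates 2σ²/n. The SE is inflated by 1/√(1−ρ), which is 1.20, 1.41 and 1.83 for ρ = 0.3, 0.5 and 0.7. Hold d=0.50 fixed on the scale of the paired difference. The stacked critical value is about 2.287 (75 degrees of freedom), so the paired statistic, centred near 3.162, must clear:

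- ρ=0.3: 2.287 × 1.195 = 2.73, power about Φ(0.43) = 67%
- ρ=0.5: 2.287 × 1.414 = 3.23, power about Φ(−0.07) = 47%
- ρ=0.7: 2.287 × 1.826 = 4.18, power about Φ(−1.01) = 16%

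Simulation, which allows for sampling variation in the SE, gives about 68%, 49% and 19%. A separate run gave 67%, 51% and 20%.

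**4. Difference regression, centred covariates.** Regress D = nightmare minus index on age, sex and duration, each minus its mean. The intercept is again the mean difference, tested on n−4 degrees of freedom. With no gain in residual variance, power is 79.1% (n=40) and 88.4% (n=50). Simulation gave 79-81% at n=40 and 88.6% at n=50.

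**5. The same regression, uncentred.** The intercept becomes the contrast at age 0 and duration 0, with an SE about 3.8 times larger under the assumed covariate distributions. Its power is about 8% (n=40) or 9% (n=50).

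**6. Duration slope.** At alpha 0.05, the partial correlation detectable with 80% power is 0.41 (n=40) or 0.375 (n=50) by the t-test. By Fisher's z it is tanh(2.80/√37) = 0.43 or tanh(2.80/√47) = 0.39.

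**The case against.** The best defence is that the Power analysis names a paired t-test, so a competent analyst would respect the pairing. With complete pairs the estimated contrast is then the right one under any of these models, and redundant covariates do it no harm. That holds for the point estimate. It does not settle the standard error or the test, because the analysis paragraph never carries the pairing over.

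Three stronger readings are tempting, and the documents do not support them.

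- A reader might infer that the plan never examines whether the nightmare's advantage depends on time since trauma. Exploratory 1A includes duration as a predictor of a stronger nightmare than index response, although the outcome is dichotomised and duration is not the focal term. A difference regression for Hypothesis 2 would also estimate a duration slope.
- A reader might take such a gradient to be the study's own prediction, since the rationale calls nightmares "of greater immediacy and salience than the more temporally distant index trauma". That is a statement about averages. A gradient with years is a reasonable inference, but no aim or hypothesis states it. Duration is also observational and may track age and chronicity.
- A reader might expect power of about 8%. That requires regressing differences, leaving the covariates raw and testing the intercept, which the plan does not say it will do. The figure is only a caution against omitting the centring.

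**Conclusion.** The Hypothesis 2 analysis is under-specified. As main effects the named covariates cannot change the contrast; this is exact for complete pairs and needs no assumption. The power loss is conditional: it applies if the regression is run on unpaired script-level rows and a participant's two responses are positively correlated. The 68%, 49% and 19% figures depend on the assumed correlations. The error is towards missing a real difference rather than declaring a false one.

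The documents do not establish that the unpaired model will be used, only that the wording permits it and fits the power calculation poorly. The primary analysis of both primary outcomes should not rest on that unstated choice, so the text should be changed. A named duration test is optional. The difference between 40 completers in the Power analysis and 50 in Recruitment is a separate matter and does not affect this conclusion.

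**What to change.** In Statistical analyses, state that for each primary outcome and each secondary region the within-person nightmare-minus-index difference in baseline-corrected response is regressed on mean-centred age, sex and duration since trauma, and that the intercept is the Hypothesis 2 test. A mixed model with a participant intercept and script-by-centred-covariate terms is equivalent. Describe the secondary comparisons as between scripts rather than groups; the false discovery rate step is unchanged.

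Optionally, report the duration slope with its confidence interval as an exploratory estimate on the continuous outcomes, alongside the dichotomised version in Exploratory 1A. State that it has 80% power only for correlations of about 0.38-0.43 at alpha 0.05.

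The cost is one or two sentences and three degrees of freedom, with no new data. Relative to the plain paired t-test, power moves from 79.3% to 79.1% with 40 completers and from 88.5% to 88.4% with 50.
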